2.2.2.2 Laboratory Evaluations

- CBC with differential
- Chemistry panels (as noted) or specific analyte including: Creatinine and potassium (i.e., or Acute Care Panel); calcium and phosphate (i.e., or Mineral Panel); ALT, AST, total bilirubin (i.e., or Hepatic Panel)
- Lactic dehydrogenase (LDH), uric acid
- Coagulation panel, including: PT/INR and aPTT
- CMV/EBV
- Hepatitis Serologies will include hepatitis C antibody, hepatitis B surface antigen, and hepatitis B core antibody. If hepatitis B core antibody, hepatitis B surface antigen, or hepatitis C antibody is positive, then PCR to quantitate hepatitis B DNA or hepatitis C RNA must be performed (within 28 days of enrollment).
- Pregnancy test: Urine or serum pregnancy test for women of childbearing potential. If positive, pregnancy must be ruled out by ultrasound to be eligible.

2.2.2.3 Other Assessments and Procedures

- ECG: 12-lead ECG will be done in triplicate (\geq 1 minute apart). Subjects should be in supine position and resting for at least 10 minutes before study-related ECGs.

2.3 PARTICIPANT REGISTRATION AND STATUS UPDATE PROCEDURES

2.3.1 NCI Registration Procedures

Registration and status updates (e.g., when a participant is taken off protocol therapy and when a participant is taken off-study) will take place per CCR SOP ADCR-2, CCR Participant Registration & Status Updates found at:

<https://ccrod.cancer.gov/confluence/pages/viewpage.action?pageId=73203825>.

2.3.2 For Participating Site Registration

Registration and status updates (e.g., when a participant is taken off protocol therapy and when a participant is taken off-study) will take place per CCR SOP MI-3, CCR Participating Site Participant Registration & Status Updates found

<https://ccrod.cancer.gov/confluence/pages/viewpage.action?pageId=73203825>. When a participant has a status change (e.g., subject screened on the study, does not meet eligibility criteria and is removed from the study, participant is taken off protocol therapy or off study, etc.), the Participant Status Update Form will be supplied by the CCR study coordinator. Send the completed form to the CCR study coordinator.

2.3.3 Screen Failures

Screen failures are defined as participants who consent to participate in the clinical trial but are not subsequently assigned to the study intervention or entered in the study. A minimal set of screen failure information is required to ensure transparent reporting of screen failure participants, to meet the Consolidated Standards of Reporting Trials (CONSORT) publishing requirements and to respond to queries from regulatory authorities. Minimal information includes demography, screen failure details, eligibility criteria, and any serious adverse event (SAE).

Individuals who do not meet the criteria for participation in this trial (screen failure) because of a laboratory parameters may be rescreened.

2.3.4 Treatment Assignment (for registration purposes only)

Cohort

Number	Name	Description
1	Cohort 1	Participants with newly diagnosed moderate or severe chronic GvHD requiring systemic immunosuppression

Arm

Number	Name	Description
1	Arm 1	Ibrutinib as a continuous daily dose by mouth

Randomization and Arm Assignment

Participants in Cohort 1 will be directly assigned to Arm 1.

2.4 BASELINE EVALUATION

Tests or evaluations performed during screening and that are within the window for prior to treatment do not need to be repeated. All of the following to be performed within 7 days before treatment.

2.4.1 Clinical Evaluations

- History and Physical Exam
- Concomitant medication review

- Karnofsky performance score ([Appendix B](#)).
- Physical examination to include: general appearance of the subject, weight, examination of the skin, eyes, ears, nose, throat, lungs, heart, abdomen, extremities, musculoskeletal system, nervous system, and lymphatic system. Vital signs will include blood pressure, heart rate, respiratory rate, and body temperature.
- Chronic GvHD Activity Assessment (Clinician) Form A ([Appendix F](#)).

2.4.2 Laboratory Evaluations

- CBC with differential
- Chemistry panels (as noted) or specific analyte including: Creatinine and potassium (i.e., or Acute Care Panel); calcium and phosphate (i.e., or Mineral Panel); ALT, AST, total bilirubin (i.e., or Hepatic Panel)
- Others: Lactic dehydrogenase (LDH), uric acid
- Serum Immunoglobulins: IgA, IgG and IgM levels.

2.4.3 Other Assessments and Procedures

- Participant Self-Assessments: All subjects in the study will complete the Chronic GvHD Activity Assessment-Patient Self Report-Form B, Lee Chronic GvHD Symptom Scale and SF36 Form ([Appendix G](#)).
- Pulmonary Function Tests (PFTs): Subjects should be evaluated for oxygen saturation or have PFTs, if not performed ≤ 3 months prior to study treatment initiation. It is not a part of inclusion/exclusion criteria.
- Non-contrast chest CT (if clinically indicated)

3 STUDY IMPLEMENTATION

3.1 STUDY DESIGN

This is a multi-center, two-stage, phase 2 study.

Subjects with newly diagnosed moderate or severe chronic GvHD according to the NIH criteria, who need systemic therapy, will be started on ibrutinib as a continuous daily dose of 420 mg by mouth. Treatment will continue in cycles consistent of 28 days on outpatient basis.

Participants with response at 6 months (CR+PR) will continue therapy until 12 months.

Participants who have a perception of benefit from ibrutinib therapy may continue on ibrutinib past the 12-month timepoint, based also on investigator discretion and discussion for up to 24 months.

Subjects may continue on stable doses of their immunosuppressive medications with the intent to taper it. See Section [4.1](#).

Addition of any systemic immunosuppressive therapy aimed at controlling chronic GvHD symptoms is prohibited and will be considered treatment failure. Participants in need of additional systemic immunosuppressive therapy will be taken off ibrutinib treatment.

Subjects may remain on topical therapy for chronic GvHD (See Section [4.2](#)).

Abbreviated Title: Ibrutinib for Chronic GvHD

Version Date: 4/26/2023

One steroid pulse (i.e., prednisone equivalent of 0.5-2 mg/kg/day) is allowed (See Section [4.1.2](#)).

Up to 28 evaluable subjects will be enrolled and treated for up to 24 months. Enrollment will occur in 2 stages: in the first stage 14 subjects will be enrolled, and if ≥ 4 subjects have a response (CR+PR at 6 months) the accrual will continue until a total of at least 25 evaluable subjects have been enrolled. As it may take 3 to 6 months to determine if a subject has experienced a response, a temporary pause in the accrual may be necessary to ensure that enrollment to the second stage is warranted.

Evaluation of chronic GvHD diagnosis per NIH criteria ([Appendix A](#)) and Chronic GvHD Organ Specific Staging and Global Scoring ([Appendix D](#) and [Appendix E](#)) will be performed at screening. Chronic GvHD Organ Specific Staging and Global Scoring ([Appendix D](#) and [Appendix E](#)) evaluations will be repeated at 9 months and 12 months, and every 3 months until off treatment.

Chronic GvHD Activity Assessment (Clinician) Form A ([Appendix F](#)) will occur at baseline, at 6 weeks and then 3, 6, 9 and 12 months from the start of ibrutinib by the bone marrow transplant physician and/or nurse practitioner trained in chronic GvHD assessments.

[figure not shown]
Response will be assessed according to the 2014 NIH Consensus Criteria ([Appendix H](#)) and as defined under Section [6.3.1](#) Response Criteria.

Participant self-assessments will occur at cycle 1 day 1, at 6 weeks and then 3, 6, 9 and 12 months from the start of ibrutinib ([Appendix G](#)).

Research blood samples will be collected for correlative science at the start of treatment with ibrutinib, and at 6 weeks, 3, 6, and 12 months from the start of ibrutinib therapy.

The post-treatment follow-up phase will begin once a subject discontinues ibrutinib treatment.

Study Schema:

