10.2 SAMPLE SIZE DETERMINATION

The primary objective of this trial is to determine the overall response rate of ibrutinib as a first-line treatment for subjects with newly diagnosed chronic GvHD based on the response at or before 6 months, according to the 2014 NIH Consensus Criteria. In similar subjects who ordinarily would receive steroid treatment, the clinical response rate using NIH criteria may typically be on the order of 30-40%. The goal would be to determine if using ibrutinib would rule out a 20% response rate and target a rate of 45%. For these subjects, the trial will be conducted using an optimal two-stage phase II trial design (Simon R, Controlled Clinical Trials 10:1-10, 1989) in order to rule out an unacceptably low PR+CR rate of 20% ($p_0=0.20$) in favor of an improved response rate of 45% ($p_1=0.45$). With $\alpha=0.10$ (probability of accepting a poor treatment=0.10) and $\beta = 0.10$ (probability of rejecting a good treatment=0.10), this first stage will enroll 14 evaluable subjects, and if 0 to 3 of the 14 have a clinical response, then no further subjects will be accrued. If 4 or more of the first 14 subjects have a response, then accrual would continue until a total of 25 evaluable subjects have been enrolled. As it may take 3 to 6 months to determine if a subject has experienced a response, a temporary pause in the accrual may be necessary to ensure that enrollment to the second stage is warranted. If there are 4 to 7 subjects with a response out of 25 subjects, this would be an uninterestingly low response rate. If there were 8 or more of 25 (32%) who experienced a response, this would be sufficiently interesting to warrant further study in later trials. Under the null hypothesis (20% response rate), the probability of early termination is 69.8%.

It is expected that approximately 1-2 subjects per month may enroll on this trial; thus, it is anticipated that 1.5 to 2 years may be required for accrual of up to 25 evaluable subjects. In order to allow for up to 3 inevaluable subjects and screen failures (screening will occur on this protocol), the accrual ceiling will be set at 40 (3 for inevaluable participants and 12 for screen failures).

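### Section 3.1 and the précis allow 26 to 28 evaluable participants, but section 10.2 gives a go rule only for 25; if more than 25 are counted, the stated alpha or power may not hold

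*Combined protocol and SAP*

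**What the plan says.** Section 10.2 (Sample Size Determination) describes an optimal two-stage design with a null response rate of 20% and a target of 45%. Alpha is given as "probability of accepting a poor treatment=0.10" and beta as "probability of rejecting a good treatment=0.10". Stage 1 has 14 evaluable participants and stops at 0 to 3 responders. With 4 or more, "then accrual would continue until a total of 25 evaluable subjects have been enrolled". The go rule is "If there were 8 or more of 25 (32%) who experienced a response"; 4 to 7 of 25 is a no-go. The accrual ceiling of 40 allows 3 for inevaluable participants and 12 for screen failures.

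Section 3.1 (Study Design) gives a different final size: "the accrual will continue until a total of at least 25 evaluable subjects have been enrolled". The same paragraph sets a maximum of 28 evaluable participants, and so does the Design part of the précis. Section 10.4.2 bases the primary analysis on evaluable participants, without limiting it to the first 25. No cut-off is given for 26, 27 or 28.

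There is also a smaller difference in wording. Section 3.1 says "in the first stage 14 subjects will be enrolled", where section 10.2 says 14 evaluable.

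**The concern.** A two-stage rule has its error rates only at the sample sizes for which it was calculated. Section 10.2 fixes the final size; section 3.1 and the précis leave it open between 25 and 28. Response may take 3 to 6 months to determine and accrual is expected at 1 to 2 per month, so participants enrolled as cover could themselves prove evaluable. The final count could then pass 25 without any departure from section 3.1.

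At stake is the go/no-go conclusion. With 8 responders among 26, 27 or 28, the result passes by count (8 or more) but fails by percentage (8/26 = 30.8%, 8/27 = 29.6%, 8/28 = 28.6%, all below 32%). The plan does not say which applies, so the choice could fall to someone who already knows the result.

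**Working it through.** **Inputs (section 10.2 unless noted).** p0 = 0.20; p1 = 0.45; alpha and beta 0.10 each; stage 1 n = 14, continue if at least 4 respond; final N = 25, go if at least 8 respond. Section 3.1 and the précis: N up to 28.

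**Formula.** For final size N and cut-off c,

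P(go) = Σ over x = 4 to 14 of Bin(x; 14, p) × P[Bin(N − 14, p) ≥ c − x].

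At p = 0.20 this is the exact alpha; at p = 0.45 it is the exact power.

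**Step 1: reproduce the plan.** The probability of at most 3 responders of 14 at p = 0.20 is 0.698, matching the stated 69.8%. An exhaustive search up to N = 40 returns 3/14 and 7/25 as the optimal design, as stated. For alpha at N = 25, c = 8:

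- x = 4: 0.17197 × 0.16114 = 0.0277
- x = 5: 0.08599 × 0.38260 = 0.0329
- x = 6: 0.03224 × 0.67788 = 0.0219
- x = 7: 0.00921 × 0.91410 = 0.0084
- x ≥ 8: 0.0024

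The sum is 0.0933. The same sum at p = 0.45 gives 0.9026. Both stated error rates are met.

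**Step 2: one more evaluable participant, cut-off still 8.** At N = 26 stage 2 has 12 participants:

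- x = 4: 0.17197 × 0.20543 = 0.0353
- x = 5: 0.08599 × 0.44165 = 0.0380
- x = 6: 0.03224 × 0.72512 = 0.0234
- x = 7: 0.00921 × 0.93128 = 0.0086
- x ≥ 8: 0.0024

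The sum is 0.1077, above 0.10.

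**Step 3: both readings at each permitted size.** As a proportion, 32% of 26, 27 and 28 is 8.32, 8.64 and 8.96, so the cut-off is 9 each time.

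| N evaluable | Cut-off 8: alpha / power | Cut-off 9: alpha / power |
|---|---|---|
| 25 | 0.093 / 0.903 | 0.043 / 0.846 |
| 26 | 0.108 / 0.914 | 0.053 / 0.872 |
| 27 | 0.122 / 0.921 | 0.064 / 0.891 |
| 28 | 0.136 / 0.927 | 0.076 / 0.905 |

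At 26 and 27, cut-off 8 fails alpha and cut-off 9 fails power. A lower cut-off raises alpha further and a higher one lowers power further, so with the gate of 4 of 14 no cut-off meets both. At 28, cut-off 9 meets both.

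**Step 4: how often the choice matters.** The two readings differ only when exactly 8 respond. At p = 0.20 that probability is the difference between the alphas: 0.1077 − 0.0533 = 0.054 at N = 26, 0.1221 − 0.0642 = 0.058 at 27, and 0.1364 − 0.0758 = 0.061 at 28. At p = 0.45 it is the difference between the powers: 0.914 − 0.872 = 0.042, 0.921 − 0.891 = 0.030 (0.031 before rounding), and 0.927 − 0.905 = 0.022. It is largest for a true rate near 0.30, at about 0.13.

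**Step 5: which size the ceiling implies.** 25 + 3 + 12 = 40 is the arithmetic of section 10.2. On it, 28 is the number eligible for treatment, and 28 evaluable is reached only if none of them is inevaluable.

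**The case against.** The statistical section is clear by itself: 25 is the stopping number, the three extra places are replacements, and the cut-off of 8 is never applied to any other denominator. On that reading the design is correct. The documents give no inevaluability rate and no plan to over-enrol, so a final count of 26 to 28 is a possibility and not a forecast. The choice between 8 and 9 matters in few trials, a go means only that further study is warranted, and 80% and 95% confidence intervals are reported in any case.

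Most of this stands and limits the point. It does not remove it. No order of precedence between sections 3.1 and 10.2 is stated, section 3.1 describes how accrual is run, and two places expressly allow up to 28 evaluable participants.

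Two stronger readings are tempting, and the documents support neither:

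- A reader might infer that the trial is planned with alpha above 0.10. That requires both that a 26th evaluable participant enters the decision and that the cut-off stays at 8. The plan leaves this case unspecified; it does not adopt it.
- A reader might infer from section 3.1 that stage 1 is judged on 14 enrolled participants, some of them inevaluable, with a loss of power. Section 10.2 explicitly says 14 evaluable, and section 3.1 speaks of evaluable participants in the preceding sentence. The shorter phrase is best read as shorthand.

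**Conclusion.** The point holds as a conflict over final sample size and decision threshold. At exactly 25 evaluable participants the design is sound. If 26 to 28 are counted, keeping 8 responders gives alpha 0.108 to 0.136 against the stated 0.10. Reading the rule as 32% keeps alpha at 0.053 to 0.076, but power falls short of 0.90 at 26 (0.872) and 27 (0.891). The excess is small at 26 and about a third over the stated alpha at 28.

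These figures assume independent responses at the stated 20% and 45%, a stage-1 gate of 4 or more of 14 evaluable, and a decision that uses all evaluable participants. The last is permitted by section 3.1 and the précis and not excluded by section 10.4.2, but it is not certain to occur. The change should be made because it is cheap and is best settled before the final count is known.

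**What to change.** - **Section 3.1:** change the stage-2 target from at least 25 evaluable to 25 evaluable. As a wording alignment only, change 14 subjects to 14 evaluable subjects.
- **Section 3.1 and the précis:** replace up to 28 evaluable with 25 evaluable (up to 28 treated, allowing for 3 inevaluable). If only the stage-2 target were edited, the contradiction would remain.
- **Section 10.2:** add that the stage-1 and final decisions use the first 14 and the first 25 evaluable participants in order of enrolment, and that any further evaluable participants are included in the reported estimate and in safety but not in the go/no-go decision.

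This retains the exact alpha of 0.093 and power of 0.903 and adds no participants. The cost is that up to three participants do not contribute to the formal decision, and the reported estimate may have a larger denominator than the decision, which the report should label.

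Alternative, only if the decision is to be made on exactly 28 evaluable participants: keep 28 and pre-specify 9 or more of 28 (alpha 0.076, power 0.905). Under the present ceiling, 40 − 28 = 12 places would then have to cover both screen failures and inevaluable participants.

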3.2 DRUG ADMINISTRATION

For this study we will use an ibrutinib dose of 420 mg (3 x 140 mg capsules) taken once a day on every day of every cycle.

Ibrutinib capsules should be swallowed whole and should not be broken, chewed or opened. Each dose of ibrutinib should be taken at approximately same time each day with 8 ounces (approximately 240 mL) of water. If a dose of ibrutinib is missed, it should be taken as soon as possible on the same day. If it is missed for the entire day, it should not be made up.

Missing < 20% doses in the first six months is allowed. Treatment with ibrutinib will be discontinued if the subject has missed ≥ 20% doses in the first six months of the study.

Participants will be asked to keep a medication diary ([Appendix I](#)). The first dose will be delivered in the clinic on Day 1, after which subsequent dosing is typically on an outpatient basis. Ibrutinib will be dispensed to subjects in bottles at each visit. Unused ibrutinib dispensed during previous visits must be returned to the site and drug accountability records updated at each visit. Returned capsules must not be redispensed to anyone.

3.2.1 Dose Adjustments for participants on CYP3A4 inhibitors

Participants who are treated with certain medications that are mild and moderate CYP3A4 inhibitors will start ibrutinib at a lower dose.

A list of common CYP3A inhibitors and inducers is provided in [Appendix C](#). For further information, please refer to the current version of the ibrutinib IB and examples of inhibitors, inducers, and substrates can be found at <http://medicine.iupui.edu/clinpharm/ddis/main-table/>.

Drug	Ibrutinib dose modification
• Mild CYP3A inhibitors	420 mg once daily. No dose adjustment required
• Moderate CYP3A inhibitors	420 mg once daily. No dose adjustment required
• Voriconazole at any dose or • Posaconazole at doses less than or equal to suspension 200 mg BID	280 mg once daily
• Posaconazole suspension 200 mg TID or 400 mg BID • Posaconazole IV injection 300 mg once daily • Posaconazole delayed-release capsules 300 mg once daily	140 mg once daily
• Other strong CYP3A inhibitors	Avoid concomitant use. If these inhibitors will be used short-term (such as anti-infectives for seven days or less), interrupt IMBRUVICA

If these medications are later discontinued, ibrutinib dose may be increased to 420 mg.

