4.3 ANCILLARY THERAPY AND SUPPORTIVE CARE

Ancillary therapy and supportive care for chronic GvHD is permitted and recommended as outlined in the NIH Consensus Development Project 2014 Ancillary Therapy and Supportive Care Working Group Report. Use of topical or organ specific medications to treat or prevent bronchiolitis obliterans (e.g., inhaled steroids/azithromycin/montelukast) or GI acute GvHD (e.g., budesonide or beclomethasone) will not be considered systemic treatment for chronic GvHD; however, each such organ specific or topical intervention must be carefully recorded and reported in the final study data report.

Use of neutrophil growth factors (e.g., filgrastim and pegfilgrastim) or red blood cell growth factors (erythropoietin) is permitted per institutional policy. Transfusions may be given in accordance with institutional policy.

Infection is the most common cause of mortality in participants with chronic GVHD and infection prophylaxis requires special emphasis. The immune defects in chronic GVHD are broad, encompassing macrophage function, antibody production, and T cell function. Prevention, early diagnosis, and prompt treatment of infections are essential to the supportive care of participants with chronic GVHD. Infection disease prevention and management guidelines will be according the NIH Consensus Development Project 2014 Ancillary Therapy and Supportive Care Working Group Report and can be modified by the respective institutional guidelines.

While standard guidelines for aspergillosis prophylaxis in participants on ibrutinib do not exist, we will implement following generally recommended strategy in this protocol:

- a) If participant is on more than 0.20 mg/kg prednisone equivalent per day we recommend receiving isavuconazole (or an alternate agent) prophylaxis;
- b) If participant is on single agent ibrutinib or lower doses of steroids than 0.20 mg/kg prednisone equivalent +/- any other immunosuppressive agent, the decision will be left to the clinician based on the clinical risk assessment in a given participant.

Clinical vigilance for invasive fungal infections will be pursued in all participants. We recommend checking serum galactomannan at scheduled clinic visits and exert low threshold for imaging studies and early BAL when suspicion exists. We also recommend checking trough isavuconazole levels at each visit if feasible or at least couple times earlier at the protocol driven follow up appointments.

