4.4 MEDICATION TO BE USED WITH CAUTION

4.4.1 CYP3A Enzyme Inhibitors/Inducers

Ibrutinib is metabolized primarily by CYP3A4.

A list of common CYP3A inhibitors and inducers is provided in [Appendix C](#). For further information, please refer to the current version of the ibrutinib IB and examples of inhibitors, inducers, and substrates can be found at <http://medicine.iupui.edu/clinpharm/ddis/main-table/>. This website is continually revised and should be checked frequently for updates. Avoid concomitant use of strong CYP3A inducers ([Appendix C](#)). Consider alternative agents with less CYP3A induction and transition to a new agent within 4 weeks of study treatment initiation. Dose modifications for participants on CYP3A4 inhibitors are listed in Section [3.2.1](#).

Avoid grapefruit and Seville oranges during ibrutinib treatment, as these contain moderate inhibitors of CYP3A.

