16.3 APPENDIX C: INHIBITORS AND INDUCERS OF CYP3A

Inhibitors of CYP3A are defined as follows. A comprehensive list of inhibitors can be found at the following website: <http://medicine.iupui.edu/clinpharm/ddis/table.aspx>. The general categorization into strong, moderate, and weak inhibitors according to the website is displayed below. Refer to Section 4.4.1 and 14.1.7 on instructions for concomitant use of CYP3A inhibitors and inducers with study medications.

Inhibitors of CYP3A	Inducers of CYP3A

Strong inhibitors:
 
INDINAVIR NELFINAVIR RITONAVIR CLARITHROMYCIN ITRACONAZOLE KETOCONAZOLE NEFAZODONE SAQUINAVIR TELITHROMYCIN
 
Moderate inhibitors:
 
aprepitant erythromycin diltiazem flucanazole grapefruit juice Seville orange juice verapamil
	
Weak inhibitors:
 
cimetidine
 
All other inhibitors:
 
amiodarone NOT azithromycin chloramphenicol boceprevir ciprofloxacin delavirdine diethyl-dithiocarbamate fluvoxamine gestodene imatinib mibepradil mifepristone norfloxacin norfluoxetine star fruit telaprevir troleandomycin voriconazole
 
Carbamazepine Efavirenz Nevirapine Barbiturates Glucocorticoids Modafinil Oxcarbazepine Phenobarbital Phenytoin Pioglitazone Rifabutin Rifampin St. John's Wort Troglitazone

Source: <http://medicine.iupui.edu/clinpharm/ddis/table.aspx>

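### Section 3.2.1 calls for a lower starting dose with certain mild and moderate CYP3A4 inhibitors, but its own table gives both classes the full 420 mg

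*Combined protocol and SAP*

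**What the plan says.** Section 3.2 sets the reference dose at 420 mg, as three 140 mg capsules, once daily throughout each cycle. The Précis allows reductions to 280 mg and 140 mg.

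Section 3.2.1 then deals with CYP3A4 inhibitors. Its lead sentence reads "Participants who are treated with certain medications that are mild and moderate CYP3A4 inhibitors will start ibrutinib at a lower dose". The table that follows has two rows for these classes: "Mild CYP3A inhibitors 420 mg once daily. No dose adjustment required" and "Moderate CYP3A inhibitors 420 mg once daily. No dose adjustment required". Further rows give 280 mg or 140 mg with voriconazole and with posaconazole, depending on the posaconazole dose and form. The last row covers the other strong inhibitors, to be avoided or, for short courses, handled by interrupting ibrutinib.

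Section 4.4.1 gives no dose of its own: "Dose modifications for participants on CYP3A4 inhibitors are listed in Section" 3.2.1. Appendix C sorts drugs into strong, moderate, weak and all other inhibitors, and sends the reader to 4.4.1 and 14.1.7.

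**The concern.** The lead sentence and the table address the same participants and give different instructions. A site that acts on the sentence starts some participants on mild or moderate inhibitors below 420 mg. A site that acts on the table starts all of them at 420 mg. In a multi-center, single-arm study, similar participants could then begin on different doses and be pooled into one response rate, with the difference arising from the drafting.

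There is also a safety side. Section 1.2.2.2 reports that in Study MCL3002 atrial fibrillation and any hemorrhage showed a significant relationship with ibrutinib exposure. The instruction that governs exposure should therefore be unambiguous. The documents give no figure for how far mild or moderate inhibitors change ibrutinib exposure, so they do not show which of the two instructions carries the greater risk.

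**Working it through.** The plan states no figure to reproduce here. The check is a comparison of texts, with one small calculation for scale.

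**Step 1: sentence against table (both in 3.2.1)**

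| Inhibitor group | Lead sentence | Table |
|---|---|---|
| Mild | lower dose for certain drugs, amount not given | 420 mg, no adjustment |
| Moderate | lower dose for certain drugs, amount not given | 420 mg, no adjustment |
| Voriconazole, posaconazole | not named | 280 mg or 140 mg |
| Other strong | not mentioned | avoid, or interrupt ibrutinib for short use |

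The mild and moderate rows have no exceptions. If the sentence covers even one mild or moderate drug, it contradicts its row.

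**Step 2: can the sentence mean the two azoles?** These are the only drugs with a reduced dose. The next row speaks of *other* strong inhibitors, which places the drugs above it in the strong class. On that reading the sentence describes as mild or moderate two drugs that the table treats as strong.

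**Step 3: does another section settle it?**
- *4.4.1* refers to 3.2.1 and adds no dose.
- *Appendix C* lists voriconazole under all other inhibitors, which is neither strong, moderate nor weak. Posaconazole does not appear in the text available for this review.
- *Exclusion 2.1.2.7* bars recent or continuous use of strong inhibitors and relies on Appendix C for the class. If the azoles are strong, as the table implies, participants who need them continuously are excluded although 3.2.1 gives them doses. If they are not strong, the table's last row is mislabelled.
- *14.1.7* points to a dosing table through a broken reference. It then says the dose should return to 420 mg once antifungals with CYP3A properties stop, without limiting this to the two azoles. Section 3.2.1 says only that the dose may be increased.

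None of these sections ranks the sentence above the table, or the table above the sentence.

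**Step 4: scale.** The sentence gives no amount. The only lower levels in the table are 280 mg and 140 mg:
- 280 / 420 = 0.67, a 33% lower daily dose
- 140 / 420 = 0.33, a 67% lower daily dose

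These show how large the gap would be if the sentence meant one of those levels. They are not doses that the sentence prescribes.

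**The case against.** The best defence rests on the word *certain*. The sentence does not cover all mild and moderate inhibitors, and it may have been meant for voriconazole and posaconazole alone. Appendix C does not list voriconazole as strong, and 14.1.7 ties the return to 420 mg to stopping antifungals. Read that way, every group has one dose. This is a plausible account of the intent. It fails as a reading of the text, because the table's last row implies that the two azoles are strong and Appendix C calls neither of them mild or moderate.

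A second defence is practical. The sentence has no milligram value, so a site has to turn to the table, which does. That stands in part, because it makes divergent dosing less likely. A directive sentence with no precedence rule still leaves the choice to the site.

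A reader might infer more than the documents support:
- *That the sentence lowers the dose for every mild or moderate inhibitor.* The word *certain* limits it.
- *That a known number of participants is affected.* The documents give no share of participants on these drugs.
- *That the cross-reference in 4.4.1 is wrong.* It leads correctly to 3.2.1. The broken reference is in 14.1.7.
- *That the C1D15 pharmacokinetic sample comes too late to protect participants.* The pharmacokinetic section uses those samples to correlate exposure with response and toxicity, and non-NIH plasma may be shipped at the end of the trial. They were never a dosing safeguard.
- *That the silence on isavuconazole is part of the contradiction.* Section 4.3 says "we recommend receiving isavuconazole (or an alternate agent) prophylaxis" above 0.20 mg/kg prednisone equivalent, and the drug is named in neither 3.2.1 nor Appendix C as available here. But 3.2.1 refers to the investigator's brochure and a website, and Appendix C to a fuller website list. The gap is a minor, separate clarification.

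**Conclusion.** The point holds as an internal inconsistency, and Section 3.2.1 is wrong as written. Its lead sentence and its table cannot both describe the starting dose for certain mild and moderate CYP3A4 inhibitors, and no other section resolves the conflict. The subject is the starting dose of the study drug, so it needs correcting even though the defect is one of text.

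The effect on the trial cannot be quantified from the documents. The dose gap would be 33% or 67% on the assumption that the sentence meant one of the two lower levels in the table, and the number of participants concerned is unknown. The two-stage design, its sample size and its error rates do not depend on this point. Nor does it undermine a fixed-dose comparison, since dose reductions are already part of the design. The placing of voriconazole and posaconazole in the strong class is inferred from the wording of the table's last row.

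**What to change.** The sponsor should make one amendment covering these items, with the clinical content left to its own clinical pharmacology:

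1. Reconcile the lead sentence of 3.2.1 with the table, so that each inhibitor class or named drug has a single starting-dose instruction. Either text may be the one that changes.
2. State the class of voriconazole and posaconazole, and make Appendix C and exclusion 2.1.2.7 agree with it. Use the same class names in both places (3.2.1 says mild, Appendix C says weak).
3. Repair the broken table reference in 14.1.7 so that it leads to the 3.2.1 rule. Align the two statements on returning to 420 mg, which say *may* in 3.2.1 and *should* in 14.1.7.
4. As a separate minor clarification, state the class of isavuconazole.

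The cost is a short text amendment and notice to sites. Visits, sample size and analysis do not change.
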